6.2. Safety Endpoints

- *Adverse events, including monitoring of targeted events including, but not limited to:*
 - *Serious adverse event.*
 - *Anticholinergic effects such as dry mouth, dry eyes and constipation.*
 - *Central nervous system (CNS) effects such as behavioral changes (eg, aggression), decreased cognitive function, headache, seizures, somnolence.*
 - *Visual effects such as accommodation disorder, blurred vision, and amblyopia.*
- *Visual acuity and accommodation tests.*
- *Cognitive function by the Child Behavior Checklist (CBCL) and Grooved Pegboard Test (GPT).*
- *Vital Signs, including heart rate in the context of age-appropriate norms.*
- *Urinary Tract Infection (UTI), as evidenced by urinalysis, urine microscopy, culture and sensitivity.*
- *Clinical Laboratory Evaluations in the context of age-appropriate norms, with particular reference to liver function tests and renal chemistry.*
- *Post-void residual volume (PVR) in subjects not performing clean intermittent catheterization (CIC), or with >1 UTI during the study.*

6.2.1. Adverse Events

Adverse event information will be collected for all subjects. Information that will be collected includes: nature of event, whether event was serious; date of onset; date of cessation or event continuing; severity of event; relationship of event to study drug; action taken regarding study drug due to the event; clinical outcome of event.

Any events occurring following the start of study drug of fesoterodine or increasing in severity will be counted as treatment emergent. Events that occur in the oxybutynin-treatment period in Cohort 1 of Study A0221047 will NOT be attributed to fesoterodine, unless they started in the oxybutynin-treatment period in Cohort 1 of Study A0221047 and became more severe in the fesoterodine-treatment period.

6.2.2. Vital Signs

Blood pressure, temperature and pulse rate should be measured at each clinic visit. This schedule of measurements should provide adequate indication of any clinically relevant changes. However, if vital signs show a clinically relevant change from baseline of Study A0221047, then safety monitoring will occur at a minimum of monthly intervals, or more

frequently as clinically appropriate, until the abnormality resolves. The measured results will be assessed in the context of age appropriate norms.

Temperature may be taken via oral, tympanic or axillary routes as per local accepted practice. Digital devices are permitted; however, mercury thermometers should not be used. The same method as Study A0221047 should be used for the subject throughout the study.

Blood pressure should be measured using a pediatric or appropriately sized sphygmomanometer in the sitting/resting position with the subject's arm supported at the level of the heart, and recorded to the nearest mmHg. The same arm (preferably the dominant arm) as Study A0221047 will be used throughout the study.

The same size blood pressure cuff as Study A0221047, which has been properly sized and calibrated, will be used to measure blood pressure each time. The use of automated devices for measuring blood pressure and pulse rate are acceptable, although, when done manually, pulse rate will be measured in the brachial/radial artery for at least 30 seconds.

6.2.3. Physical Examination

A physical examination will be performed at each clinic visit, and will include the following systems:

- *General appearance (including weight);*
- *Skin;*
- *Head, eyes, ears, nose, and throat; including visual acuity and accommodation (see [Section 6.2.5](#));*
- *Respiratory;*
- *Cardiovascular;*
- *Gastrointestinal;*
- *Musculoskeletal;*
- *Neurological.*

If physical examinations show a clinically relevant change from baseline of the precedent Study A0221047, then safety monitoring will occur at a minimum of monthly intervals, or more frequently as clinically appropriate, until the abnormality resolves. Any clinically significant negative changes from the entry examination will be recorded as adverse events.

6.2.4. Weight Measurements

Weight will be recorded at each clinic visit. All weight measurements should be standardized using the same equipment and measuring technique for an individual subject. Any clinically significant change in weight should be reported as an adverse event.

Even if the body weight of subjects with ≤ 25 kg at baseline of the precedent Study A0221047 increase > 25 kg during Study A0221047 or this study, they should maintain the same dose and formulation.

6.2.5. Visual Acuity and Accommodation

Visual acuity will be assessed for each eye using the Snellen method, using an optotype that is appropriate to the child's intellectual development at each clinic visit.

Amplitude of accommodation will be assessed by the push up test to assess minimum focusing distance at each clinic visit. The subject will focus on a single letter of the 20/40 line of an eye chart (appropriate optotype) and this will be moved slowly toward the subject until it blurs. At this point the distance from eye to letter will be measured. An attempt will be made to record 3 measurements and entered in the eCRF.

For both visual acuity and accommodation assessments the same optotype will be used for a specific subject throughout the study to ensure standardization and validity.

6.2.6. Post-Void Residual Volume (PVR)

PVR urine volume in subjects not performing CIC will be assessed using trans-abdominal ultrasound (eg, bladder scan) immediately after urination. If at Visit 1 (Week 0 [Week 24 in Study A0221047]), the measured volume is higher than 20 mL (see exclusion criterion 6), the subject should not be included.

Assessment of PVR in subjects performing CIC should also be carried out in the event that they experience > 1 UTI during the Study A0221047 and this study.

6.2.7. Clinical Laboratory Evaluation

Safety laboratory tests will be performed at each clinic visit, or as needed to follow-up on significant findings.

Table 2. Safety Laboratory

Hematology	Chemistry	Urinalysis	Other
Hemoglobin Hematocrit RBC count Platelet count WBC count with differential as below: Total neutrophils (Abs) Eosinophils (Abs) Monocytes (Abs) Basophils (Abs) Lymphocytes (Abs)	GOT (AST) GPT (ALT) GGT Total and direct bilirubin Alkaline phosphatase LDH CPK BUN Creatinine ^a Uric acid Total protein Sodium Potassium Chloride Albumin Corrected calcium Bicarbonate Phosphorus Glucose (non fasting)	Urine will be tested for the following using a urine dipstick: pH Specific gravity Leukocyte esterase Nitrites Glucose Protein Blood Ketones Urine microscopy, culture and sensitivity ^b	Pregnancy Test ^c (urine)

a. When indicated, the investigator may request calculation of an estimated GFR using the Schwartz equation $GFR = (k \times H)/Cr$ where k = constant, H = Height (length) and Cr = Creatinine. In this case, the laboratory will need to be provided with the subject's height in cm.

b. Urine microscopy, culture and sensitivity to be performed in the event of the presence of symptoms (eg, fever, flank pain), positive leucocytes and/or nitrites on urinalysis, or if the subject has a documented history of vesicoureteral reflux (VUR).

c. Females of childbearing potential only (≥ 9 years old or have experienced menarche, whichever is earlier). Pregnancy tests may also be repeated as per request of Institutional Review Board (IRB)/Ethics Committee (EC) or if required by local regulations.

6.2.8. Childhood Behavior Checklist (CBCL)

The CBCL is a questionnaire by which a child's problem behaviors and competencies can be assessed. This instrument will be completed by the parent or caregiver. The CBCL can also be used to measure a child's change in behavior over time or following a treatment. The first section of this questionnaire consists of 20 competence items and the second section consists of 120 items on behavior or emotional problems. For the purpose of this trial, the parent or caregiver, should preferably be the same person at each visit, and will be asked to complete 113 items on behavior and emotional problems. The parent or caregiver will be asked to describe their child as of 'now'.

The CBCL will be completed at each clinic visit.

6.2.9. Grooved Pegboard Test (GPT)

The GPT is a manipulative dexterity test that assesses psychomotor speed, fine motor control, and rapid-visual motor coordination. It consists of a small board of 25 holes with randomly positioned slots. Pegs with a key along one side must be rotated to match the

hole before they can be inserted. Time to completion, number of pegs dropped, and number of pegs placed correctly are scored.

The GPT will be assessed at each clinic visit.

6.3. Other Endpoints

None.

6.4. Covariates

None.

7. HANDLING OF MISSING VALUES

No imputation for missing data will be planned in efficacy and safety analysis.

In the case that the data of patient's background in Study A0221047 is used for the analysis of this study, handling of missing data in Study A0221047 will be employed in this study.

8. STATISTICAL METHODOLOGY AND STATISTICAL ANALYSES

8.1. Statistical Methods

Efficacy endpoints and treatment-emergent adverse events will be summarized using merged data of Study A0221047 and Study A0221109. When the longitudinal changes are analyzed for the merged data, baseline will be Visit 1 (Screening) or Visit 2 (Day 1) of Study A0221047. Demographics and baseline characteristics including medical history, prior drug/Non-drug treatments will use baseline information at Visit 1 (Screening) or Visit 2 (Day 1) of Study A0221047. Other safety endpoints will be summarized for the data of Study A0221109 alone, and baseline will be Week 0 of Study A0221109.

Treatments will be labeled as follows:

Cohorts of Study A0221047 (for analysis using the merged data of Study A0221047 and A0221109)

Cohort 1

Cohort 2

Treatment groups of Study A0221047 (for analysis using the merged data of Study A0221047 and A0221109, demographics and baseline characteristics)

Fesoterodine 4 mg Tab

Fesoterodine 8 mg Tab

Oxybutynin->Fesoterodine 4 mg Tab

Oxybutynin->Fesoterodine 8 mg Tab

Fesoterodine 2 mg BIC

Fesoterodine 4 mg BIC

Treatment group at baseline in Study A0221109 (for analysis using the data of Study A0221109 alone)

Fesoterodine 4 mg Tab (A0221109)

Fesoterodine 8 mg Tab (A0221109)

Fesoterodine 2 mg BIC (A0221109)

Fesoterodine 4 mg BIC (A0221109)

The cohorts and the treatment groups of Study A0221047 will be used for data summaries of efficacy endpoints and treatment-emergent adverse events. The treatment groups at baseline in Study A0221109 will be used for data summaries of the safety endpoints excluding adverse events, although the dosage can be reduced to the lower dose at each clinic visit for subjects on the higher dose.

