8.2. Statistical Analyses

8.2.1. Analysis of Efficacy Data

For the following efficacy analyses, data will be summarized for the total of treatment groups, each cohort and each treatment group of Study A0221047, using the merged data of Study A0221047 and Study A0221109. *Subgroup analyses will be conducted that exclude oxybutynin treatment group in cohort 1 of A0221047 from the total for all efficacy endpoints if any subjects who were randomized to oxybutynin group in A0221047 are in FAS.*

All efficacy endpoints of continuous data and their change from baseline will be summarized descriptively by each visit according to 8.1.1.

The presence of IDC will be summarized by each visit according to 8.1.2.

Listing tables will be provided at each timepoint from baseline visit of A0221047 to final visit of this study for all efficacy endpoints of observed values and changes from baseline with

subjects information (ie., subject ID, gender, age, body weight at baseline of A0221047, cohort of A0221047, randomized treatment group in A0221047 and treatment history from the A0221047 start to the end of this study).

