8.2.2. Analysis of Safety Data

Tables and listings of safety and demographic data, including adverse events and medical history will be reported in accordance with current Pfizer standards using baseline information at start of A0221047.

Treatment emergent adverse events will be summarized for the total of treatment groups, each cohort and each treatment group of Study A0221047, using the merged data of Study A0221047 and Study A0221109. Treatment emergent adverse events (PT; preferred term) will be also summarized by the period of the onset time from the start of the fesoterodine treatment (0 – 12 weeks (1-84 days), 13 – 24 weeks (85-168 days), 25 – 36 weeks (169-252 days), in or after 37 weeks (\geq 253 days)).

For the following safety analyses, data will be summarized for each treatment group at baseline of Study A0221109, using the data of Study A0221109 alone.

Vital Signs

Blood pressure and pulse rate and their change from baseline will be summarized descriptively for each treatment group, by each visit according to 8.1.1.

Listings of all vital signs will also be created.

Visual Acuity and Accommodation

Visual acuity (LogMAR units) and accommodation (the distance for each eye at which vision becomes blurred – the mean of triplicate measurements) and their change from baseline will be summarized descriptively for each label, by each visit according to 8.1.1.

Listings of visual acuity and accommodation will also be created.

For Visual Acuity, LogMAR units will be derived from the Snellen ratios recorded on the CRF, as shown in the table below. The decimal is the Snellen ratio (whether it is recorded in metres or feet) expressed as a decimal and $\text{LogMAR} = \text{Log}_{10}(1/\text{decimal})$ (recorded to 1 d.p.). Due to the limited space available in the CRF, the Snellen ratio '20/12.5' will be recorded as '20/13', however this should still be converted to a decimal value of 1.60 and a LogMAR value of -0.2 as shown in the table below. If the Snellen Visual Acuity has been recorded in any other format than those shown below, the appropriate conversion to decimal will be determined prior to database lock.

Table 3
Equivalent visual acuity measurements

Snellen visual acuity					
20 ft	6 m	4 m	Decimal	MAR ^a	LogMAR
20/640	6/192	4/128	0.03	32	1.5
20/500	6/152	4/100	0.04	25	1.4
20/400	6/120	4/80	0.05	20.0	1.3
20/320	6/96	4/63	0.063	16	1.2
20/250	6/76	4/50	0.08	12.5	1.1
20/200	6/60	4/40	0.10	10.0	1.0
20/160	6/48	4/32	0.125	8.0	0.9

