10. APPENDICES

Appendix 1. DATA DERIVATION DETAILS

Appendix 1.1. Definition and Use of Visit Windows in Reporting

There were no visit windows defined for Study A0221047. The target observation of “Week 12 from Day 1 of Study A0221047” will also be that taken at a time closest to when the scheduled visit should have occurred.

Visit windows for after Study A0221109 are defined.

Table 4. Visit Windows for Efficacy Endpoints

Visit Label	Endpoint	Definition [Day window]
A0221047:Day1	Urodynamic Assessments Bladder Diary	Same definitions of A0221047 will be used.
A0221047:Week12	Urodynamic Assessments Bladder Diary	Same definitions of A0221047 will be used.
A0221047:Week52/ A0221109:Week28	(for Fesoterodine arms in Study A0221047) Urodynamic Assessments Bladder Diary	= An assessment where ‘Date of assessment’ – ‘Date Day 1 of Study A0221047’ + 1 = [310, 407]
A0221047:Week 64/ A0221109:Week40	(for Oxybutynin arm in Study A0221047) Urodynamic Assessments Bladder Diary	= An assessment where ‘Date of assessment’ – ‘Date Day 1 of Study A0221047’ + 1 = [408, 491]
Final Visit	Urodynamic Assessments Bladder Diary	= The last assessment where ‘Date of assessment’ – ‘Date Day 1 of Study A0221047’ + 1 > 169

Table 5. Visit Windows for Safety Endpoints

Visit Label	Endpoint	Definition [Day window]
A0221047:Week24/ A0221109:Day1	Vital Signs Visual Acuity and Accommodation PVR Clinical Laboratory Evaluation CBCL GPT	= An assessment where 'Date of assessment' – 'Date Week 0 of Study A0221109' + 1 is in [-20, 42]
A0221047:Week36/ A0221109:Week12	Vital Signs Visual Acuity and Accommodation PVR Clinical Laboratory Evaluation CBCL GPT	= An assessment where 'Date of assessment' – 'Date Week 0 of Study A0221109' + 1 is in [43, 140]
A0221047:Week52/ A0221109:Week28	Vital Signs Visual Acuity and Accommodation PVR Clinical Laboratory Evaluation CBCL GPT	= An assessment where 'Date of assessment' – 'Date Week 0 of Study A0221109' + 1 is in [141, 238]
A0221047:Week64/ A0221109:Week40	(for Oxybutynin arm in Study A0221047) Vital Signs Visual Acuity and Accommodation PVR Clinical Laboratory Evaluation CBCL GPT	= An assessment where 'Date of assessment' – 'Date Week 0 of Study A0221109' + 1 is in [239, 322]
Final Visit	Vital Signs Visual Acuity and Accommodation PVR Clinical Laboratory Evaluation CBCL GPT	= The last assessment after 'Date of assessment' – 'Date Week 0 of Study A0221109' + 1 >= 43

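### Safety tables other than adverse events take an on-treatment baseline (Week 0 of A0221109), so none shows change from before fesoterodine to 1 year

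*SAP*

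**What the plan says.** SAP 8.1 sets two baselines. For data merged across the two studies, which means efficacy and treatment-emergent adverse events, it says: "When the longitudinal changes are analyzed for the merged data, baseline will be Visit 1 (Screening) or Visit 2 (Day 1) of Study A0221047". For everything else in safety it says: "Other safety endpoints will be summarized for the data of Study A0221109 alone, and baseline will be Week 0 of Study A0221109".

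SAP 8.2.2 repeats the second rule ahead of vital signs, vision, PVR, laboratory evaluation, CBCL and GPT: "data will be summarized for each treatment group at baseline of Study A0221109, using the data of Study A0221109 alone". In Appendix 1.1, the first row of Table 5 (safety windows) is "A0221047:Week24/ A0221109:Day1". Table 4 (efficacy windows) has rows for Day 1 and Week 12 of A0221047, each with the entry "Same definitions of A0221047 will be used".

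Efficacy listings reach back to the start: "Listing tables will be provided at each timepoint from baseline visit of A0221047 to final visit of this study for all efficacy endpoints". Adverse events are also tabulated "by the period of the onset time from the start of the fesoterodine treatment".

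One sentence points the other way. SAP 8.2.2 opens by saying that safety and demographic tables and listings "will be reported in accordance with current Pfizer standards using baseline information at start of A0221047".

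Protocol section 3 and the schedule of activities place Week 0 of A0221109 at the Week 24 visit of A0221047. Protocol 1.2 and SAP section 2 give the study rationale as safety and tolerability over 1 year.

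**The concern.** Long-term safety and tolerability is the primary objective, yet the change tables for the measured safety endpoints start partway through treatment. Inclusion criterion 1b requires entrants to have tolerated fesoterodine, so Week 0 is an on-drug value for all of them. For PVR it is also a selected value, because exclusion criterion 6 removes non-catheterizing subjects above 20 mL at that visit.

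A shift in pulse, accommodation, PVR, laboratory values, CBCL or GPT that arose in the first months on drug and then persisted would be built into the baseline and would appear as no change. Clinically significant findings should still surface as adverse events. What could go unseen is mainly drift too small to be recorded as one. Meanwhile efficacy, the secondary objective, is tabulated from the pre-treatment baseline.

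**Working it through.** **Inputs**

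- Week 0 of A0221109 = Week 24 of A0221047 (Protocol 3).
- Final Visit: extension Week 28 for the fesoterodine arms, Week 40 for the oxybutynin arm; the schedule of activities labels these Weeks 52 and 64 from the A0221047 baseline.
- The oxybutynin arm runs to Week 40 so that 1 year of fesoterodine data is obtained (Protocol 3). The date of the switch is not given.
- Table 5, first row: date of assessment − date of Week 0 + 1 lies in [−20, 42].
- AE onset periods in SAP 8.2.2: days 1–84, 85–168, 169–252, and 253 onward.
- About 9 subjects expected (Protocol 9.1); six A0221047 treatment labels (SAP 8.1).

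**Plan's own timeline**

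- Fesoterodine arms: 24 + 28 = 52 weeks, as stated.
- Oxybutynin arm: 24 + 40 = 64 weeks, as stated.
- Taking 1 year as 52 weeks, fesoterodine starts in the oxybutynin arm at Week 64 − 52 = 12 of A0221047 (inferred). That gives 24 − 12 = 12 weeks on fesoterodine before Week 0.

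**Share of the fesoterodine year before and after the baseline**

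| | Before Week 0 | Longest change shown |
|---|---|---|
| Fesoterodine arms | 24/52 = 46.2% | 28/52 = 53.8% |
| Ex-oxybutynin (inferred) | 12/52 = 23.1% | 40/52 = 76.9% |

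The ±2-week window on the Final Visit makes total exposure 50 to 54 weeks and does not alter the point.

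**Can a pre-treatment value enter through the visit window?**

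- Nominal fesoterodine day at Week 0: 24 × 7 + 1 = 169 in the fesoterodine arms; 12 × 7 + 1 = 85 in ex-oxybutynin subjects.
- Earliest date accepted: date − Week 0 + 1 = −20, so the date is 21 days before Week 0.
- Fesoterodine day on that date: 169 − 21 = 148, or 85 − 21 = 64. Both are on treatment, so none can.

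**Against the SAP's own AE periods**

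Days 1–84 and 85–168 both precede Week 0 in the fesoterodine arms; days 1–84 do so in ex-oxybutynin subjects. The adverse event tables cover these periods, and the tables of measured endpoints do not.

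**How much of an effect is hidden**

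This depends on its time course, which the documents do not give. An effect arising only after Week 0 loses 0%. If it built up linearly over 52 weeks (an assumption), 46% or 23% would be lost. An effect that had plateaued by Week 0 loses 100%.

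**The opening sentence of SAP 8.2.2**

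Read literally, it would put the baseline at the start of A0221047 for all safety tables. The explicit rule in 8.1, the repeated rule later in 8.2.2 and the absence of any earlier row in Table 5 all contradict that reading. The SAP's change summary ties the A0221047 baseline to demographics and baseline characteristics. The sentence therefore conflicts with 8.1 and does not fill the gap.

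**The case against.** The strongest reply is that the difference from efficacy has a practical cause. In the extension, urodynamics and the bladder diary are scheduled only at the Final Visit, and Table 4 has no Week 24 row, so the planned efficacy analysis has no Week 0 value to use. The measured safety endpoints do have one. Adverse events count from the first fesoterodine dose because that is how treatment emergence is defined. Protocol 9.3 also extends only the adverse event tables back to the start of A0221047 and groups the other endpoints by treatment at the baseline of this study.

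Other safeguards exist: age-appropriate norms, tabulation of laboratory abnormalities, listings of these endpoints, subject narratives, review by the external data monitoring committee, and individual monitoring of vital signs, physical examination and liver tests against the A0221047 baseline. With about 9 selected completers, growing and without a control group, change over a year is hard to interpret. A0221047 may itself report its first 24 weeks.

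Much of this stands and limits the seriousness. The visit schedule explains why the two baselines differ, and selection and maturation would qualify any 1-year change. But none of the safeguards supplies a change from pre-treatment to 1 year. Protocol 9.3 fixes the grouping and names no baseline for change. The time span of the narratives is not stated. A group summary of Weeks 0–24 in A0221047 cannot simply be added to a Week 0–28 summary here, because this study enrols only Japanese completers. A small sample favours subject-level listings back to pre-treatment, which efficacy already has.

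**Conclusion.** The concern holds, for the safety tables other than adverse events. Their baseline falls after 46% of the fesoterodine year in the fesoterodine arms and after an inferred 23% in ex-oxybutynin subjects, and no planned table of these endpoints includes a pre-treatment value. The primary objective is therefore described by on-treatment values and on-treatment change only. No effect size is claimed.

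The study is descriptive, with no hypotheses or decision rules, so nothing in the plan is invalidated; it should be fixed because the remedy costs little. The ex-oxybutynin figures assume that 1 year means 52 weeks of fesoterodine, and such subjects may not enrol. What A0221047 reports for its own 24 weeks cannot be checked from these documents.

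**What to change.** 1. Keep the change-from-Week-0 tables by A0221109 treatment group; they suit late effects.
2. In SAP 8.1 and 8.2.2 add, on merged data by A0221047 treatment group, observed values and change from the A0221047 pre-treatment baseline (Screening or Day 1) to each extension clinic visit and the Final Visit, for every endpoint measured at that baseline. Add the matching row to Table 5.
3. Extend the subject listings of these endpoints back to the A0221047 baseline, as 8.2.1 does for efficacy. With 9 subjects over up to six labels (9/6 = 1.5 per label), the listings will be more informative than the summaries.
4. Show ex-oxybutynin subjects separately. The four A0221109 labels pool them with the fesoterodine arms, so a Week 28 row can mix 52 and an inferred 40 weeks of exposure. Use the last value before the switch as their baseline where one exists. Otherwise use A0221047 Day 1, noting that the change spans about 64 weeks, of which an inferred 12 (12/64 = 19%) were on oxybutynin.
5. State that uncontrolled change in growing children, all of them completers who tolerated the drug, mixes drug effect, maturation and selection.
6. Reword the opening sentence of 8.2.2 to agree with 8.1.

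The cost is SAP wording and one extra descriptive set for about 9 subjects, with no new assessments; the two studies' data are already merged for efficacy and adverse events. First confirm what A0221047 collected. The documents imply a baseline for vital signs, physical examination and liver tests. For vision, PVR, CBCL, GPT and any safety value before the switch, it must be checked.

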2. STUDY OBJECTIVES AND ENDPOINTS

2.1. Objectives

2.1.1. Primary Objective

- To investigate the safety and tolerability of fesoterodine following once daily long-term treatment in Japanese pediatric NDO subjects.

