4.1. Inclusion Criteria

Subject eligibility should be reviewed and documented by an appropriate member of the investigator's study team before subjects are included in the study.

Subjects must meet all of the following inclusion criteria to be eligible for enrollment into the study:

1. Subjects who completed 24 week treatment and all visit procedures in the precedent Study A0221047, and who met the following criteria;
 - a. No findings suggestive of worsening condition of NDO compared to baseline of the precedent Study A0221047.
 - b. Tolerated the dose of fesoterodine.
Subjects who did not tolerate the higher dose of fesoterodine (8 mg/day for subjects >25 kg or 4 mg/day for subjects ≤25 kg) well but were not withdrawn can be included; for the A0221109 study the dose can be reduced to low dose of the same formulation (4 mg/day tablet for subjects >25 kg or 2 mg/day BIC for subjects ≤25 kg) (See Section 3).
2. Evidence of a personally signed and dated informed consent document indicating that the subject (or a legally acceptable representative/parent(s)/legal guardian) has been informed of all pertinent aspects of the study. In addition, an assent from the subject will be obtained when appropriate, and when the potential subject is capable of providing assent.
3. Female subjects who are of child-bearing potential (defined as ≥9 years old or have experienced menarche, whichever is earlier) must not be intending to become pregnant, currently pregnant, or lactating. The following conditions apply:
 - a. Subjects of childbearing potential must have confirmed negative pregnancy tests during Study A0221047.
 - b. Subjects of child-bearing potential must agree to use effective contraception during the period of the trial and for at least 28 days after completion of treatment. Effective contraception includes abstinence.
 - c. Sexually active male subjects must agree to use effective contraception during the period of the trial and for at least 28 days after completion of treatment.

Further details of the definition of child-bearing potential and effective contraception may be found in Section 4.3.

4. Swallowing:
 - a. Subjects >25 kg must already have the ability to swallow tablets whole, without chewing or crushing. The first dose of medication will be given in clinic under observation, and any subject not able to swallow tablets will be excluded from the study.

- b. Subjects ≤ 25 kg can either swallow the capsules whole or sprinkle on food.

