5. STUDY TREATMENTS

5.1. Allocation to Treatment

This is an open label study. As a rule, all subjects should continue to receive the allocated dose in Study A0221047 until the end of the trial, unless a safety/toleration problem occurs. But, only if the investigator judges that the continued treatment with low dose (4 mg/day for subjects >25 kg or 2 mg/day for subjects ≤25 kg) is useful to the subject although the high dose (8 mg/day for subjects >25 kg or 4 mg/day for subjects ≤25 kg) is likely to cause some problems with tolerability, and the subject wants the treatment with the low dose, the dosage may be reduced to the low dose at each clinic visits. Dose should not be increased to the high dose.

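### No planned summary counts high-to-low dose reductions, and after a reduction in the extension the high-dose safety columns mix doses; for reductions at Week 0, SAP 5.5 and 8.1 conflict

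*SAP*

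**What the plan says.** The primary objective (Protocol 2.1.1) is "To investigate the safety and tolerability of fesoterodine following once daily long-term treatment in Japanese pediatric NDO subjects". The study rationale (Protocol 1.2, repeated in SAP 2) names each tablet and capsule strength and a duration of 1 year.

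The only dose change described is from high to low. Under Protocol 5.1, where the high dose is likely to be poorly tolerated and the child wants the low dose, "the dosage may be reduced to the low dose at each clinic visits"; going back up is ruled out. Inclusion criterion 1b (Protocol 4.1) also allows a change at entry: "for the A0221109 study the dose can be reduced to low dose of the same formulation".

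The table columns are set in SAP 8.1. For TEAEs: "The cohorts and the treatment groups of Study A0221047 will be used for data summaries of efficacy endpoints and treatment-emergent adverse events". For everything else in safety: "The treatment groups at baseline in Study A0221109 will be used for data summaries of the safety endpoints excluding adverse events", with the rider "although the dosage can be reduced to the lower dose at each clinic visit for subjects on the higher dose". SAP 8.2.2 repeats the TEAE grouping: "Treatment emergent adverse events will be summarized for the total of treatment groups, each cohort and each treatment group of Study A0221047". Protocol 9.3 also groups by randomised group or by group at extension baseline; neither follows the dose after a reduction.

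For each adverse event the study collects "action taken regarding study drug due to the event" (SAP 6.2.1). SAP 8.2.2 specifies no summary of it, and dose reduction is not among the safety endpoints in Protocol 2.2.2 or SAP 6.2. Treatment history is a column in the by-subject efficacy listings (Protocol 9.2.2, SAP 8.2.1). The protocol also promises a narrative for each subject; the SAP text does not carry this over.

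SAP 5.5 treats a subject who does not start on the A0221047 randomised dose as having taken the incorrect treatment, and reports that subject by actual treatment in all safety analyses.

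**The concern.** A step down from the high dose bears directly on whether that dose can be kept up for a year. The plan permits it, acknowledges it when fixing the columns, and then counts it nowhere. A reader of the planned tables cannot see how many children started on the high dose and stayed on it, or when and why the others came off.

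The fixed columns add a second difficulty. A high-dose column that contains post-reduction time describes children who started on the high dose, not time spent on it. TEAEs are also tabulated by onset period (SAP 8.2.2), with the last two periods covering weeks 25 to 36 and week 37 onward. A fall in events there could be read as adaptation when part of it reflects a lower dose.

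**Working it through.** **Expected size of the study.** Protocol 9.1 expects about 9 children: 9 in cohort 2 plus a few in cohort 1, less 12.5% drop-out. With 1, 2 or 3 children in cohort 1, (9 + few) × 0.875 gives 8.75, 9.63 or 10.5, so the stated figure reproduces. The split by dose is not given.

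**Reduction at Week 12 (fesoterodine arms).** Inputs: the extension runs to Week 28, which is week 52 from A0221047 baseline. Clinic visits are Weeks 0, 12 and 28 (Protocol 3.1), so Week 12 is the only scheduled clinic visit between entry and the Final Visit.

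- Low-dose weeks under the high-dose label: 28 − 12 = 16.
- Share of extension weeks: 16/28 = 57%.
- Share of total weeks: 16/52 = 31%.
- By-visit safety values: the Week 28 value is entirely a low-dose value.

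**Weight of one child.** Assuming 2 to 5 children in a high-dose column, one reduced child is 1/5 to 1/2 of it, or 20% to 50%. This range is an assumption. A cohort 1 column could be smaller still, because a few children are spread over up to four labels.

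**Direction.** For illustration only, take the adult dry mouth rates in Protocol 1.2 (35% at 8 mg, 19% at 4 mg), treat them as 12-week risks with constant hazard, and reduce the dose at total week 36.

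- Weekly hazards: −ln(0.65)/12 = 0.0359 (high) and −ln(0.81)/12 = 0.0176 (low).
- Kept on the high dose for 52 weeks: 1 − exp(−0.0359 × 52) = 85%.
- As the column would record it: 1 − exp(−(0.0359 × 36 + 0.0176 × 16)) = 79%.
- High-dose time only, 36 weeks: 1 − exp(−0.0359 × 36) = 73%.

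The column figure is below what a year on the high dose would give and above what occurred on the high dose. The sign of the distortion depends on the comparison intended.

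**Reduction at Week 0.** In the non-AE safety tables, if the baseline group means the dose started, the child is already in a low-dose column. For TEAEs, two rules apply:

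- SAP 8.1 and 8.2.2: by A0221047 group. Then 28/52 = 54% of the child's weeks are low-dose weeks in a high-dose column.
- SAP 5.5, read literally: by actual treatment. The TEAE data are merged from the start of A0221047, so events from the first 24 weeks (24/52 = 46%), on the high dose, could move to a low-dose column.

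**Reach of the listings.** The Full Analysis Set needs an efficacy observation after extension baseline (SAP 5.1). Urodynamics and the diary are scheduled only at the Final Visit or early withdrawal (Schedule of Activities), and urodynamics at withdrawal requires no missed dose in the previous 3 days (Protocol 6.4). A child who withdraws early can therefore be in the Safety Analysis Set but absent from the listings that show dose history.

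**The case against.** Grouping by starting dose is a legitimate convention and the SAP discloses it. There are no hypotheses and no planned dose comparison. With about 9 children, the listings and narratives would let a reader count most reductions by hand. SAP 8.2.2 also refers to the sponsor's reporting standards, which may include such counts and cannot be seen here. Reduction is not a pure tolerability outcome either: Protocol 5.1 allows it in anticipation of a problem and requires the child's wish. Splitting very small columns by dose at onset will give sparse cells.

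Much of this stands. It rules out the reading that dose reductions go unreported: individual dose history is planned, and what is missing is a summary. It is also a reason to keep the starting-dose columns. It does not remove the gap. The listings are for efficacy and follow the Full Analysis Set, the narratives are not specified in the SAP, and neither document says that the sponsor's standards count reductions. Because no recorded event is needed for a reduction, the action-taken field alone could miss some.

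A reader might also infer that the high dose will look better tolerated than it was. The documents do not support that. The event that prompts a reduction stays in the high-dose column, and later low-dose events are added to it, so a crude count can overstate high-dose events as easily as a later row can understate them.

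**Conclusion.** The plan does not specify a summary of dose reductions, although tolerability is the primary objective and the rationale is dose-specific over 1 year. Under SAP 8.1, data after a reduction in the extension stay in the high-dose column. For a Week 12 reduction in a child from the fesoterodine arms, that is 57% of extension weeks, 31% of total weeks and all of the Week 28 value. These shares rest only on the visit schedule. The effect on a column also depends on its size and on how many children are reduced, neither of which the documents give. The direction of the distortion is not established.

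For Week 0 reductions the finding is a contradiction between SAP 5.5 and 8.1. The 54% share should not be quoted as a settled consequence, since it applies only if 8.1 governs. This is an inexpensive improvement to the analysis plan and implies no fault in the dosing rule.

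**What to change.** In SAP 8.2.2, for the Safety Analysis Set:

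- (a) Summarise, by starting dose, the number, week and reason of dose reductions and of withdrawals due to adverse events.
- (b) Beside the planned TEAE table, show TEAEs by dose at onset with child-weeks on each dose, and flag post-reduction values in the safety listings.
- (c) Reconcile SAP 5.5 with 8.1, so that a protocol-permitted reduction at Week 0 is not handled as a misallocation in one section and by A0221047 group in another.

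Keep the planned starting-dose columns. Do not repeat the high-dose columns with post-reduction values removed: the later rows would then hold only children who stayed on the high dose, a group selected for tolerating it.

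The cost is SAP wording and a few small tables with sparse cells. Drug accountability records (Protocol 5.6), the dosing log (Protocol 7.2.10) and action taken for each event (SAP 6.2.1) are already collected. The documents do not say whether a reason for each reduction reaches the database, so it may have to be taken from the log. The dosing rule is not changed.
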